[REDACTED]							[REDACTED]
[REDACTED]							[REDACTED]
[REDACTED]							[REDACTED]
Migraine Disability Assessment (MIDAS)				X			X (week 12 only)

¹ Concomitant medications, including prophylactic and standard of care migraine medications, taken during Observation Period and rescue medication taken during the Treatment Phase should be recorded in the subject's paper diary and reviewed by study personnel at each visit. Female subjects will also record menstrual period information on the paper diary which should be reviewed by study personnel at each visit.

² The actual baseline visit date should be used for IWRS enrollment date and eligibility date.

³ Height measured at Screening Visit only. Weight, body temperature, respiratory rate, blood pressure, and heart rate will be collected at all timepoints where indicated. Sitting arterial systolic and diastolic blood pressure and radial artery pulse rate will be measured.

⁴ SAEs, AEs, and Concomitant Procedures must be reported after subject signs informed consent. SAEs should be reported from signing of consent through the 8-week Follow up Safety Visit. Non-serious AEs should be reported from signing of consent through 2-Week Follow up Safety Visit.

⁵ Subjects should finish a bottle of study medication before starting a new bottle. Study drug will be dispensed at monthly (every 4 weeks) study visits, as needed. Unscheduled visits to dispense study medication may be scheduled as needed. At the Week 12 Visit, the open-label study medication will be dispensed and subjects will be instructed not to begin taking rimegepant until confirmation from site staff pending lab results.

⁶ Subjects must take their study medication every other day, regardless of whether or not they have a migraine. Subjects must report each tablet they take in the eDiary. Doses are not required to be taken in the office on days of a study visit, however dosing requirements and compliance should be discussed with subjects at all visits.

⁷ The Observation Period to determine eligibility is 28 days +3 days. The “+3” days window is included for scheduling purposes only. Subjects with less than 24 completed eDiary reports during the Observation Period will not be considered for participation due to non-compliance with the eDiary. Subjects in the Double-blind, Treatment phase who demonstrate poor compliance will be discussed with the Sponsor and corrective training will be completed by the site with the subject.

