- **OL rimegepant treated subjects:** Enrolled subjects who received at least one dose of OL rimegepant, i.e., non-missing OL rimegepant start date.
  - **Interim subjects:** OL rimegepant treated subjects with OL rimegepant start date – DBT last date  $> 7$  days.
- **DB or OL rimegepant treated subjects:** Enrolled subjects who received at least one dose of rimegepant (DB or OL) i.e., non-missing DB or OL rimegepant start date. This corresponds to the Rimegepant Safety Analysis Set in the BHV3000-305 Protocol.
- **Follow-up subjects:** Treated subjects whose last contact date is in the follow-up safety analysis period.
- **Coronavirus Disease 2019 (COVID-19) impacted:** Enrolled subjects who are impacted by COVID-19 (see Section 9.1.2).

See Sections 7.3 and 7.4 for derived dates and analysis periods, respectively.

---

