#### 6.2.6.1 *Study Medication*

The eDiary has multiple sources of study drug exposure. Subjects are required to report study drug date/times and doses in the following 4 eDiary sources as appropriate: (1) study medication from the scheduled dosing report; (2) study medication to treat headache or aura from the evening report headache log; (3) additional study medication to treat headache or aura from the evening report headache log; or (4) study medication to treat headache or aura from the follow-up headache log. In addition, sites may report study drug dates and doses in the eDiary medication reconciliation form from missed scheduled dosing reports or evening report headache logs.

Imputed OL rimegepant to treat headache date/time will be derived for subjects who answer “yes” to the question about having already taken study medication to treat a headache on the eDiary scheduled dosing report, but do not have study drug data from any other eDiary source on the same day. Subjects with non-missing imputed OL rimegepant to treat headache date/times will be credited with taking 1 tablet of OL rimegepant on each of those days to account for missed OL rimegepant exposure from eDiary non-compliance. Otherwise, if no study drug data were reported in the eDiary on a given day (i.e., missing study drug date/time), then it is assumed that the subject did not take study drug that day. See Section 7.3 for derived dates.

A by-subject listing will present eDiary exposure (i.e., number of tablets taken) and drug accountability for randomized subjects. This listing will include all drug accountability data including treatment (DB rimegepant; DB placebo; OL rimegepant) corresponding to the kit ID, but only eDiary records with non-missing study drug start date/time and number of tablets > 0. The eDiary subcategory of question (scheduled dosing report; evening report headache log [study medication; additional study medication]; follow-up headache log; and medication reconciliation form) will also be displayed. COVID-19 visit impact code for visits impacted by COVID-19 will also be displayed (see Section 9.1.5.2).

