### **7.3 Derived Dates**

Derived dates for defining analysis periods are defined as follows:

---

- eDiary reference time/point date/time: See Section 7.6.2.1.
  - eDiary dosing dates:
    - Study drug to treat headache or during aura date/time: Complete reference time point date/time from any of the following date/time questions: study medication to treat headache or during aura from the evening report headache log or follow-up headache log; additional study medication to treat headache or during aura from the evening report headache log.
    - Imputed OL rimegepant to treat headache date/time: Complete reference time point date/time from “yes” response to question about having already taken study medication to treat headache from the scheduled dosing report. Derived only if both of the following criteria are met:
      - Reference time point date/time on or after the IWRS Week 12 kit assigned local date/time
      - There are no complete reference time point dates on the same day as the “yes” response from any of the following questions: study medication to treat headache or during aura date/time from the evening report headache log or follow-up headache log; additional study medication to treat headache or during aura date/time from the evening report headache log; date of missed scheduled dosing report or evening report headache log from the medication reconciliation form; study medication date/time from the scheduled dosing report.
    - Study drug date/time: Study drug to treat headache or during aura date/time, imputed OL rimegepant to treat headache date/time, or complete reference time point date/time from any of the following questions: date of missed scheduled dosing report or evening report headache log from the medication reconciliation form (note that time is not collected); study medication date/time from the scheduled dosing report.
      - DBT: Reference time point date/time before the IWRS Week 12 kit assigned local date/time (reference time point date before the IWRS Week 12 kit assigned local date for medication reconciliation form data) or the IWRS Week 12 kit assigned local date/time missing
      - OL rimegepant: Reference time point date/time on or after the IWRS Week 12 kit assigned local date/time (reference time point date on or after the IWRS Week 12 kit assigned local date for medication reconciliation form data)
    - Study drug start date/time: Earliest study drug date/time.

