    - Non-study medication triptan and ergotamine parameters: The reference time point date/time will be set to the last non-missing headache start date/time from evening report headache logs with finding date/time  $\leq 24$  hours at or before the follow-up headache log finding date/time.
    - Study medication for headache parameters with the same finding date/time: The reference time point date/time will be set to the study medication for headache or aura date/time, if not missing.
      - Parameters will include the following: study medication for headache or aura (yes, no); study medication for headache or aura date/time; number of tablets taken; confirm number of tablets taken (yes, no).
  - Scheduled dosing report parameters with the same finding date/time: The reference time point date/time will be set to the study medication date/time, if not missing.
-

- Parameters will include the following: took study medication today (yes, no); study medication date/time; number of tablets taken; confirm number of tablets taken (yes, no).
- Medication reconciliation form date missed and number of tablets taken parameters with the same finding date/time: The reference time point date/time will be set to the date missed, if not missing. Note that time will be missing.

Otherwise, the reference time point date/time will be set to the eDiary finding date/time.

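### SAP 7.3 classes an untimed reconciliation-form dose dated on the Week 12 kit day as open-label rimegepant, although it is expected to be the last double-blind tablet

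*SAP*

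**What the plan says.** **Dose classification.** SAP 7.3 compares timed eDiary doses with the date and time at which the Week 12 kit was assigned. Doses from the medication reconciliation form are compared by date alone. They are DBT with a "reference time point date before the IWRS Week 12 kit assigned local date for medication reconciliation form data" and OL rimegepant with a "reference time point date on or after the IWRS Week 12 kit assigned local date for medication reconciliation form data". If no Week 12 kit date exists, every dose is DBT.

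**The form.** SAP 6.2.6.1 explains that "sites may report study drug dates and doses in the eDiary medication reconciliation form from missed scheduled dosing reports or evening report headache logs". SAP 7.6.2.1 confirms that no time is available: "The reference time point date/time will be set to the date missed, if not missing. Note that time will be missing".

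**The laboratory gate.** Protocol 4.3, Table 1 footnote 5, has the OL kit handed out at the Week 12 visit, where "subjects will be instructed not to begin taking rimegepant until confirmation from site staff pending lab results". Table 2 footnote 1 and Protocol 4.3.3 say the same.

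**What follows from the dates.** SAP 7.3 takes the earliest OL dose as the OL start date. For placebo subjects this is also the rimegepant start date. SAP 3 defines OL rimegepant treated subjects as "Enrolled subjects who received at least one dose of OL rimegepant, i.e., non-missing OL rimegepant start date", and defines the DB or OL rimegepant set in the same way. The analysis periods in SAP 7.4 are built from the same start and last dates.

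**The concern.** The tie rule runs against the protocol. On the day the OL kit is assigned, the subject is still under double-blind dosing and has been told not to open the new kit. Morning dosing is preferred (Protocol 7.2.2), so a tablet taken that day will often precede the visit. If it is logged in the eDiary with a time, it is classed correctly. If the subject misses the report and the site enters the same tablet on the form, it becomes OL rimegepant.

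That one record sets a false OL start date and pulls the DBT last date back to the previous dosing day. Period boundaries, OL exposure, the rimegepant baseline of placebo subjects and, for subjects who never enter the extension, set membership all depend on these dates. I found no rule in the SAP that checks OL entry, laboratory eligibility or returned OL kits before a start date is accepted. The kit comparison in SAP 6.2.6.1 covers double-blind records only, to find subjects given the wrong double-blind drug.

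**Working it through.** The plan states no figure on this point, so the check applies its rules to constructed subjects.

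**Inputs.** Dosing is every other day (Protocol 7.2.2), taken here from study day 1. The Week 12 visit is on Day 84 plus up to 3 days (Protocol 4.3, Table 1), that is days 84 to 87. A dose then falls due on visit days 85 and 87, not on 84 or 86. Assumed for the example: visit on day 85, tablet at 08:00, kit assigned at 11:00.

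**Step 1. Placebo subject who fails the laboratory gate and takes no OL drug.**

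| | Tablet timed in eDiary | Same tablet on form, rule as written | Same tablet on form, tie to DBT |
|---|---|---|---|
| DBT last date | day 85 | day 83 | day 85 |
| OL start date | none | day 85 | none |
| Time on OL | 0 days | 85 − 85 + 1 = 1 day | 0 days |
| In OL and DB-or-OL rimegepant sets | no | yes | no |

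In the middle case the on-rimegepant safety period runs to day 85 + 7 = 92 once an OL last date is derived. Before the final lock, SAP 7.3 derives that date only if an OL or follow-up completion status is present. A rimegepant-arm subject in the same position would be wrongly placed only in the OL set.

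**Step 2. Subject who continues, first true OL dose on day 89, last on day 123.** Time on OL as written is 123 − 85 + 1 = 39 days. With the tie sent to DBT it is 123 − 89 + 1 = 35 days. The 4 extra days are the last double-blind dosing day and the wait for laboratory confirmation. SAP 7.4 also puts adverse events starting on the OL start date into the OL period and takes them out of on-DBT, so events starting on day 85 change period.

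**Step 3. MSQ and MIDAS.** For these, the on-DBT efficacy period in SAP 7.4 ends at the earlier of DBT last date + 1 day and OL start.

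- As written: min(83 + 1, 85) = day 84. A questionnaire completed on day 85 is outside.
- Tie to DBT, subject of Step 2: min(85 + 1, 89) = day 86. It is inside.

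SAP 6.3.2.3 and 6.3.2.4 require a Week 12 score from this period, and these endpoints are fifth and sixth in the hierarchy of SAP 6.1.2. The diary endpoint is not cut in this example: Month 3 ends on day 84 (SAP 6.3.1.1), and the diary period still reaches 83 + 1 = 84.

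**Step 4. Size.** The documents give no count, so the rates below are assumptions.

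- False OL start dates, both arms: 700 subjects reach Week 12, half have a dosing day on the visit date, and 1% to 5% of doses exist only on the form. 700 × 0.5 × 0.01 = 3.5; 700 × 0.5 × 0.05 = 17.5. About 4 to 18 subjects.
- Placebo subjects wrongly in the rimegepant sets: about 800 − 675 = 125 do not enter the extension, and half, 62.5, are placebo. Suppose 10% to 50% had a Week 12 kit assigned, and 1% to 10% of those have a form dose on the visit day. 62.5 × 0.10 × 0.01 = 0.06; 62.5 × 0.50 × 0.10 = 3.1.
- The same group on the first set of rates: 700 − 675 = 25 reach Week 12 without entering. 25 × 0.5 × 0.5 × 0.01 = 0.06; with 0.05, 0.31.

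**The case against.** A date-only tie has to go one way. The SAP revision history shows that the comparison with the kit date was specified on purpose in version 6.0. An early OL dose is prohibited, not impossible. Subjects with no kit assigned cannot be affected. A falsely included subject with no OL completion status would also show as ongoing in the extension disposition table (SAP 6.2.3.4), which would look odd at final lock. All of this stands, and it limits the problem. But the protocol makes a double-blind tablet the expected case on that day, and an oddity in a table does not reassign the dose.

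A reader might infer that the hepatic secondary endpoints are contaminated, because those who fail the gate have abnormal results. The documents do not show this. The on-rimegepant period begins after the start date, so a gate-failing sample drawn on the visit day is generally counted as before rimegepant. SAP 7.4 compares dates when the measurement time is missing, but does not spell out the case of a timed sample against an untimed start. Scheduled follow-up liver tests come 14 days and 8 weeks after the end-of-treatment visit. Exposure is therefore confined mainly to an unscheduled repeat or an early end-of-treatment visit within the 7 days, and to adverse events. The laboratory endpoint also needs ALT or AST above 3 × ULN with bilirubin above 2 × ULN, while the liver exclusion limits in Protocol 5.3 are above 1 × ULN.

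A reader might also infer that form entries with zero tablets create false dates, since the listing in SAP 6.2.6.1 keeps "only eDiary records with non-missing study drug start date/time and number of tablets > 0" and SAP 7.3 does not repeat that filter. Nothing in the documents shows that such entries occur, and SAP 3 requires at least one dose received. It is not part of this point.

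**Conclusion.** The tie rule gives the wrong answer for the case the protocol leads one to expect, and no other section repairs it. The effect is narrow: it needs a form dose dated on the kit day. For those subjects, in either arm, the OL start and DBT last dates are too early, with the consequences for exposure, adverse-event period and Week 12 questionnaires shown above.

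The 4 to 18 subjects are false start dates and should not be read as subjects wrongly counted as exposed. Placebo subjects who enter the extension belong in the rimegepant sets; only their dates shift. Wrong entry to the DB-or-OL set is limited to placebo subjects with a kit assigned who never took OL drug, about 0.06 to 3 under the assumed rates. For such a subject, later samples or adverse events within 7 days would count as on rimegepant. The reading of the rule is firm. The counts rest on assumptions, including that the kit is assigned on the visit day. The correction should be made, but nothing here shows that a trial conclusion would change.

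**What to change.** In SAP 7.3, class reconciliation-form dates on or before the Week 12 kit-assigned date as DBT, and only later dates as OL rimegepant. Check exceptions against OL kit accountability and the DB Subject Status CRF item on continuing to OL. Then derive the dates, analysis periods and population flags again. This changes a derivation only and implies nothing about dosing.

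The kit comparison in SAP 6.2.6.1 needs the same attention. It assigns a dose to a kit whose dispense date is on or before the dose date, so a kit-day dose newly classed as DBT would be read there as coming from the OL kit.

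Cost: no new data, but a rerun of the derived datasets. Version 10.0 of the SAP was itself modified after the final database lock, so the change would be made unblinded. It should be documented with before-and-after counts, and Week 12 report tables may need restating. A rare OL dose taken early on the kit day would be classed as DBT unless kit accountability identifies it. A full returned OL kit settles the matter for subjects who never entered the extension, but tablet counts cannot date a dose for those who continued.

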### 6.3.1.2 *Reduction in Migraine Days per Month in the OLE Phase*

The number of migraine days per month in the OLE phase will be examined relative to the number of migraine days per month in the OP for evaluable OL rimegepant mITT subjects, i.e., mITT subjects with ≥ 14 days of eDiary efficacy data (not necessarily consecutive) in both the OP analysis period and ≥ 1 month (i.e., 4-week interval) in the on-OL rimegepant efficacy analysis period. Results will support an exploratory objective.

Months in the OLE phase will be defined as:

- Month 1 (> 12 to ≤ 16 weeks; study days 85 to 112)
- Month 2 (> 16 to ≤ 20 weeks; study days 113 to 140)
- Month 3 (> 20 to ≤ 24 weeks; study days 141 to 168)
- Month 4 (> 24 to ≤ 28 weeks; study days 169 to 196)
- Month 5 (> 28 to ≤ 32 weeks; study days 197 to 224)
- Month 6 (> 32 to ≤ 36 weeks; study days 225 to 252)
- Month 7 (> 36 to ≤ 40 weeks; study days 253 to 280)
- Month 8 (> 40 to ≤ 44 weeks; study days 281 to 308)
- Month 9 (> 44 to ≤ 48 weeks; study days 309 to 336)
- Month 10 (> 48 to ≤ 52 weeks; study days 337 to 364)
- Month 11 (> 52 to ≤ 56 weeks; study days 365 to 392)
- Month 12 (> 56 to ≤ 60 weeks; study days 393 to 420)
- Month 13 (> 60 to ≤ 64 weeks; study days 421 to 448).

Analyses will be based on eDiary efficacy dates in the OP analysis period and on-OL rimegepant efficacy analysis period.

The number of migraine days per month will be prorated to 28 days, and derived as follows:

- OP: See Section 6.3.1.1.
- Month (i.e., 4-week interval) in the on-OL rimegepant efficacy analysis period:  $28 \times (\text{total number of migraine days in the month}) / (\text{total number of efficacy data days in the month})$ .  
Subjects must have ≥ 14 days of efficacy data (not necessarily consecutive) in the specified month to be evaluable.

- Overall OL rimegepant mean:  $28 \times (\text{total number of migraine days through Month 13 in the on-OL rimegepant efficacy analysis period}) / (\text{total number of efficacy data days through Month 13 in the on-OL rimegepant efficacy analysis period})$ .

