    - Efficacy date: (1) Complete reference time point date from any question from the evening report headache log or follow-up headache log, or (2) non-missing OL rimegepant date on a non-scheduled day (see Sections [7.6.2.2](#) and [7.6.2.3](#)).
    - OP start date: Earliest reference time point date from the OP epoch.
    - OP end date: Latest reference time point date from the OP epoch.
  - Miscellaneous composite dates
-

- Last DBT visit date: Maximum of the following: (1) latest eDiary reference time point date < OL rimegepant start date; (2) latest complete visit date from Visit Date CRF records without “follow-up” in foldername and visit date < OL rimegepant start date. This will be used to assess eDiary compliance.
- Last OLE visit date: Maximum of the following: (1) latest eDiary reference time point date ≥ OL rimegepant start date; (2) latest complete visit date from Visit Date CRF records without “follow-up” in foldername and visit date ≥ OL rimegepant start date. This will be used to assess eDiary compliance.
- Last DB or OL rimegepant visit date: Maximum of last DBT visit date and last OLE visit date for subjects whose as-treated treatment group is rimegepant; last OLE visit date/time for subjects whose as-treated treatment group is placebo. This will be used to assess eDiary compliance.
- Last contact date: (1) Earliest complete death date from the AE CRF, if it exists; (2) otherwise, the maximum complete date of the following: AE start/stop; COVID-19 visit only for in-person or remote visits; ECG; eDiary reference time point; informed consent; IWRS randomization; laboratory collection; menstrual period start/stop; non-study medication start/stop; physical measurement; procedure; rating scale; questionnaire; study completion/discontinuation from Subject Status CRF (DBT, OLE, follow-up); vital sign; visit.
- COVID-19 visit date: (1) Complete record date, if it exists; otherwise, complete date the visit was planned to occur for a missed visit (see Section 9.1.1).
- Death date: Last contact date derived only for subjects who died (see Section 6.5.1.1).

No imputations are performed on these derived dates. Complete dates are those with valid, non-missing day, month, and year.

See Section 7.6.2.1 for the reference time point date/time and epoch derivations.

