#### 7.6.2.2 eDiary Migraine Days

For migraine day analyses, a day of efficacy data is defined as any non-missing eDiary efficacy date (see Section 7.3).

A migraine day is defined as a day of efficacy data with either (1) or (2):

- 1) Qualified migraine headache based on the following criteria per BHV3000-305 Protocol Appendix 3:
  - “Yes” response to the question about having a headache# with complete reference time point date/time#, or non-missing headache start date/time# (see Section 7.3)
  - Lasting for  $\geq 30$  minutes, defined as any of the following:
    - “Yes” response to the question about the headache lasting  $\geq 30$  minutes#
    - Headache end date/time# – headache start date/time#  $\geq 30$  minutes, where headache end date/time and headache start date/time have the same finding date/time
    - Finding date/time# – headache start date/time#  $\geq 30$  minutes and headache end status is still continuing#, where headache start date/time and headache end status have the same finding date/time
    - Headache end date/time@ – headache start date/time#  $\geq 30$  minutes, where headache end date/time is from the follow-up headache log with earliest finding date/time  $\leq 24$  hours on or after the finding date/time of a still continuing headache from the evening report headache log
  - Meeting at least one of the following criteria (a or b):

- a.  $\geq 2$  of the following pain features based on “yes” response to questions with the same finding date/time:
    - i. Unilateral location#,
    - ii. Pulsating quality (throbbing)#,
    - iii. Moderate or severe pain intensity#
    - iv. Aggravation by or causing avoidance of routine physical activity (e.g. walking or climbing stairs)#
  - b.  $\geq 1$  of the following associated symptoms based on “yes” response to questions with the same finding date/time:
    - i. Nausea#
    - ii. Vomiting#
    - iii. Both photophobia# and phonophobia#
- 2) No qualified migraine headache but meeting either of the following criteria:
- a. Non-missing date/time of (1) study drug to treat headache or during aura#@ during the on-DBT efficacy analysis period, or (2) OL rimegepant on a non-scheduled day during the on-OL rimegepant efficacy analysis period (see Sections 7.3 and 7.6.2.3).

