- Block 2: All days on or after the first switch but before the second switch are considered to follow the second planned EOD dosing pattern. If there is only 1 switch, then all days on or after the first switch are considered to follow the second planned EOD dosing pattern.
- Block 3: All days on or after the second switch but before the third switch are considered to follow the initial planned EOD dosing pattern. If there are only 2 switches, then all days on or after the second switch are considered to follow the initial planned EOD dosing pattern.

This iterative process continues as needed.

Example:

- Subject has 26 days in the on-OL rimegepant efficacy analysis period, i.e., OL rimegepant start date on day 0 and OL rimegepant last date + 1 on day 25.
  - Scheduled report dates fall on planned OL rimegepant days 0, 2, 4, 8, 9, 11, 15, 18, 22, and 24.
    - The initial EOD dosing schedule pattern is even.
    - There are 2 switches: day 9 is the first switch and day 18 is the second switch.
    - All even days from 0 to 8 inclusive (i.e., days 0, 2, 4, 6, 8) are scheduled days.
    - All odd days from 9 to 17 inclusive (i.e., days 9, 11, 13, 15, 17) are scheduled days.
    - All even days from 18 to 24 inclusive (i.e., 18, 20, 22, 24) are scheduled days.
-

- All other days (i.e., days 1, 3, 5, 7, 10, 12, 14, 16, 19, 21, 23, and 25) are non-scheduled days.

Note that (1) imputed OL rimegepant dates and (2) OL rimegepant dates from the scheduled dosing report can only be on scheduled days. OL rimegepant dates from the evening report headache log, follow-up headache log, or medication reconciliation form can be on scheduled or non-scheduled days.

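### In the open-label phase a day with no headache log can enter the prorated rates only as a migraine day, which shifts the open-label results by an amount the plan does not report

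*SAP*

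**What the plan says.** SAP 7.3 gives two routes to an efficacy date. Clause (1) is "Complete reference time point date from any question from the evening report headache log or follow-up headache log". Clause (2), which needs open-label drug and so operates only in the open-label extension (OLE), is a "non-missing OL rimegepant date on a non-scheduled day". SAP 7.6.2.2 states that "a day of efficacy data is defined as any non-missing eDiary efficacy date", and its criterion 2a(2) makes a migraine day of "OL rimegepant on a non-scheduled day during the on-OL rimegepant efficacy analysis period".

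The OLE monthly rate in SAP 6.3.1.2 is 28 × migraine days / efficacy data days, and a month needs at least 14 efficacy days to be evaluable. The overall OLE mean has as its denominator the "total number of efficacy data days through Month 13 in the on-OL rimegepant efficacy analysis period".

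Three further places show where a dose without a log comes from:

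- SAP 6.2.6.1: "sites may report study drug dates and doses in the eDiary medication reconciliation form from missed scheduled dosing reports or evening report headache logs".
- SAP 7.6.2.3 confines imputed doses and doses from the scheduled dosing report to scheduled days, but "OL rimegepant dates from the evening report headache log, follow-up headache log, or medication reconciliation form can be on scheduled or non-scheduled days".
- SAP 7.6.2.1 lists what the form contributes: "Medication reconciliation form date missed and number of tablets taken parameters with the same finding date/time". It names no headache, severity or non-study medication item.

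The Revision History records that the efficacy date and criterion 2a were both modified in version 10.0, after the final database lock.

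**The concern.** Scaling a partial month to 28 days assumes that the days included stand for the days missing. In the observation period (OP) and the double-blind phase that rests on one condition, that a headache log exists, and a logged day can be positive or negative. Clause (2) adds a second way in for the OLE, and its entry condition is itself a migraine criterion. An unlogged day with a non-scheduled dose adds 1 to both numerator and denominator. An unlogged day without one adds to neither, whether or not it was a migraine day.

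The results at stake are the OLE change from OP, the OLE responder percentages, and the rescue and triptan/ergotamine rates, which share the denominator. Such days also count toward the 14-day floor, and so toward membership of the evaluable OL rimegepant mITT sample in SAP Section 3.

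**Working it through.** **The plan's own example.** The schedule rule in SAP 7.6.2.3 reproduces: scheduled reports on days 0, 2, 4, 8, 9, 11, 15, 18, 22 and 24 give switches at days 9 and 18, with 14 scheduled and 12 non-scheduled days out of 26. The plan gives no figure for the effect of clause (2).

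**Which days clause (2) adds.** A dose recorded in the evening or follow-up headache log already qualifies under clause (1). Scheduled-report and imputed doses cannot fall on non-scheduled days. What remains is a reconciliation-form dose on a non-scheduled day with no log.

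**Effect on total migraine days.** Let D be logged days in the month, M the migraine days among them, and k the clause (2)-only days.

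- Log-only rate: 28M/D
- SAP rate: 28(M+k)/(D+k)
- Difference: 28k(D−M)/[D(D+k)], which is positive whenever k > 0 and M < D

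| D | M | Log-only | k = 1 | k = 2 |
|---|---|---|---|---|
| 24 | 5 | 5.83 | 6.72 | 7.54 |
| 22 | 4.4 | 5.6 | 6.6 | 7.5 |
| 14 | 2.8 | 5.6 | 7.1 | – |

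The last two rows use an assumed daily migraine probability p = 0.20, so M = 0.20 × D. With k = 1 and M = pD the difference is 28(1−p)/(D+1). Over assumed ranges of p = 0.15 to 0.30 (4.2 to 8.4 days per month) and D = 14 to 26, it runs from 28 × 0.70/27 = 0.7 to 28 × 0.85/15 = 1.6. These are effects in a subject-month that contains such a day.

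**Expected effect.** The documents give neither the number of missing diary days, m, nor the share q of unlogged migraine days captured as a non-scheduled dose; both are assumed. With p = 6/28, missingness unrelated to migraine, D = 28−m and a = m·p·q, the expected SAP rate is 28(Dp+a)/(D+a). The log-only rate stays at 6.00.

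| m | q = 0.10 | q = 0.25 | q = 0.50 |
|---|---|---|---|
| 4 | 6.08 | 6.19 | 6.39 |
| 8 | 6.19 | 6.46 | 6.90 |
| 14 | 6.46 | 7.12 | 8.13 |

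Simulation agrees closely: 6.19 (m = 4, q = 0.25), 6.44 (m = 8, q = 0.25) and 6.87 (m = 8, q = 0.50). About half of OLE days are non-scheduled, so if migraine falls evenly over the schedule, q = 0.50 is near the ceiling.

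**Other rates.** A clause (2)-only day has no reported intensity, which Protocol Appendix 3 requires for a moderate to severe migraine day. It enters only that denominator: with 4 such migraine days in 24 logged days, the rate falls from 28 × 4/24 = 4.67 to 28 × 4/25 = 4.48. The OLE rescue and triptan/ergotamine rates (SAP 6.3.2.2 and 6.3.3.3) are diluted in the same way.

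**Evaluability.** A month with 13 logged days and 3 migraine days is not evaluable. One clause (2)-only day makes it evaluable, at 28 × 4/14 = 8.00.

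**If missingness depends on migraine.** Take 6 per 28 on logged days and 8 missing days with twice the daily risk. The truth is 20 × 6/28 + 8 × 12/28 = 7.71, and the log-only rate is 6.00. The SAP rate is 6.90 at q = 0.25 and 7.74 at q = 0.50.

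**The case against.** The strongest objection is that clause (2) serves the protocol. Appendix 3 counts an open-label day as a migraine day if study medication was taken during aura or to treat headache, and Protocol 7.2.2 allows non-scheduled open-label doses only as acute treatment. Dropping these days would discard migraine days that the protocol means to count, lower the open-label totals and flatter the drug. This stands as a reason not to simply delete the clause. It is not complete: the form carries no reason for the dose, and criterion 2a(2) omits the protocol's condition that a headache or aura was being treated, so an off-schedule preventive dose also counts.

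A reader might infer that the open-label migraine rates are biased upward against the truth. The documents do not support that. It holds only if diaries are missed independently of migraine; in the dependent example above, the log-only rate is further from the truth than the SAP rate.

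A reader might also infer that the effect grows in later months, or that removing the clause would put OP and OLE on equal terms. Nothing in the documents shows a time trend. The two periods already differ, because criterion 2b counts triptan and ergotamine days on treatment but not in the OP.

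Protocol 7.4 lets missing migraine data be corrected by a Data Clarification Record or the reconciliation form, and does not say how a corrected migraine-free day would be stored. The statement that unlogged days enter only as migraine days is therefore a statement about the SAP's definitions.

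**Conclusion.** The selection effect is real and follows from the definitions. Relative to the log-only rate, the direction is certain: up for total migraine days, down for moderate-or-severe, rescue and triptan/ergotamine days. Because the rates move in opposite directions, calling the rule conservative does not settle the matter.

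The size is uncertain. The 0.7 to 1.6 is conditional on an affected subject-month and is not an average over subjects. The expected shifts of +0.1 to +0.4 (4 missing days) and +0.2 to +0.9 (8 missing days) rest on a true rate of 6, capture of 10-50% and missingness unrelated to migraine. Months with as few as 14 logged days should be uncommon, since Protocol Table 2, footnote 8 has repeated poor diary compliance considered for discontinuation.

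The primary endpoint, the testing hierarchy and the sample size are untouched, because clause (2) does not operate before open-label dosing and the OLE migraine-day analyses are exploratory and descriptive. What is missing is any display that lets a reader see how much this rule, modified after the final lock, contributes.

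**What to change.** Report, by OLE month, the number of efficacy days that qualify through clause (2) alone and the number of subjects who have them.

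Present the OLE tables of migraine-day change, responder percentages, and rescue and triptan/ergotamine days in two versions: as now defined, and with both the efficacy day and the 14-day floor requiring an evening-report or follow-up headache log entry, as in the OP and double-blind phase. Criterion 2a(2) can stay in the second version: because a migraine day must be an efficacy day, dose-only days drop out, while logged days with a non-scheduled dose still count.

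The cost is one extra set of OLE tables. A few subject-months will become non-evaluable in the log-only version, and their number should be shown. No new data are needed.
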